10.5.7 In between regular visits at the Karma Study Centre

The participants can at any time in between regular visit at the Karma Study Centre contact the Karma personal with questions and issues regarding adverse events, compliance and concomitant medications. The Karma personal will give participants fast access to health care in case of need. Contact channels are phone, mail, visit or the application Karmapp designed for the study.

10.5.8 Reminders

Women will receive SMS reminders regarding their upcoming appointment and/or web-questionnaire to complete.

Women not showing up at regular visits at the Karma Study Centre or fail to submit follow-up questionnaires will be contacted to ensure compliance and to ensure that no adverse events have occurred.

10.6 Criteria for discontinuation and handling of drop-outs

The participant should be excluded from the study if, in the opinion of the Investigator, it is medically necessary, or if it is the expressed wish of the participant. Women are free to discontinue their participation in the study at any time.

A withdrawn participant is not allowed to re-enter into the study. The criteria for withdrawal are the following:

- Participant wishes to discontinue
- Participant fulfil any, in the protocol defined, exclusion criteria
- Unacceptable adverse event/side effect
- Non-compliance with the study protocol
- Participant refuses to cooperate
- Other medical reasons

Irrespective of the reason for withdrawal and whenever possible, the participant should be encouraged to return for a clinical visit at the time of or soon after discontinuation and complete all evaluations which may be necessary to assure that the participant is free from any untoward effects and to perform appropriate follow-up for any continuing medical event.

There is also a scientific value to continue investigating the effects of topical endoxifen after the participant discontinues her treatment. Women that drop out after 1 week or more, will therefore be asked to perform exit examination; follow-up questionnaire, blood sampling and exit-mammogram. The time limit of exit exams is set to 2 weeks after the participant has stopped the medication. The women are asked, in all cases, to return the remaining IMP to Karma Study Centre.

Withdrawals will not be replaced. Inclusion stops when 90 participants have been included irrespective of numbers of drop outs.

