9.1.2 Analysis of the primary endpoint (effectiveness)

The analysis of the primary endpoint qualitatively and quantitatively summarize difference in density change between baseline and at 3 and 6 months follow-up between the three arms. More specifically, the difference in density between baseline and at 3 and 6 months follow-up, respectively, for women in the placebo arm (ΔD_p) and in the two endoxifen arms (ΔD_{e1} and ΔD_{e2}), will be computed. Subsequently, the difference between ΔD_p and ΔD_{e1} as well as ΔD_p and ΔD_{e2} (at both 3 and 6 months) will be assessed.

The primary analysis will be performed on an intention to treat (ITT) basis, and a per protocol (PP) analysis will be performed as a secondary analysis. Women who stop using topical endoxifen will be encouraged to remain in the study and come in for an exit mammography. The density measured in these mammograms will be used in the analyses of the ITT population. Our experience from the Karisma-2 study is that virtually all women accept an exit mammography if choosing to withdraw from the study. However, women who drop out of the study and do not come in for additional

mammography appointments will be assumed to not have any density reduction for the ITT analysis. Sensitivity analyses where density for women who drop out is imputed based on age and density at baseline will also be performed.

Since this is a pilot study, which is not powered for showing statistical significance when testing for differences in mammographic density reduction between the treatment arms and the control arm, a simple criterion based on the difference in the mean of the density reduction across the two treatment arms and the density reduction in the control arm will be used instead. The concept mt is defined as the mean of the reduction in mammographic density across all women in the two treatment arms ($n=60$) and the mc to be the mean on the reduction in mammographic density in the control arm ($n=30$). The result of the trial as mt minus mc will be summarized.

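### Section 10.6 does not separate stopping the product from leaving the study, so non-compliance can end scheduled outcome collection in a trial whose primary analysis is ITT

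*Combined protocol and SAP*

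**What the plan says.** Section 10.6 gives six criteria for withdrawal. One is "Non-compliance with the study protocol"; unacceptable side effects are a separate one. Withdrawal is final: "A withdrawn participant is not allowed to re-enter into the study". The section then recognises scientific value in studying women after they stop, but offers a single examination: "Women that drop out after 1 week or more, will therefore be asked to perform exit examination", and "The time limit of exit exams is set to 2 weeks after the participant has stopped the medication". No later visit is described for these women, and "Withdrawals will not be replaced".

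Section 9.1.2 ranks the two analyses: "The primary analysis will be performed on an intention to treat (ITT) basis, and a per protocol (PP) analysis will be performed as a secondary" one. On stopping treatment it says: "Women who stop using topical endoxifen will be encouraged to remain in the study and come in for an exit mammography". It adds: "The density measured in these mammograms will be used in the analyses of the ITT population". Women with no further mammogram are counted as having no reduction, with imputation as a sensitivity analysis.

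Three other places bear on this:
- Section 10.7.11 calls a woman compliant if she uses more than 80% of her sachets, and treats an interruption of more than 14 days as discontinuation of treatment. Section 10.6 refers to neither rule.
- Section 9.1.3 simulates 65% good compliers with the full effect, 25% poor compliers with half the effect, and 10% dropouts.
- Appendix A has one column for early termination or withdrawal. It has no path for a woman who stops the product but keeps her scheduled visits.

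**The concern.** An ITT comparison needs outcomes collected on the same schedule whatever a woman does after randomisation. Section 10.6, followed as written, lets behaviour after randomisation close that schedule. Staff cannot both withdraw a woman for not using the product and encourage her to remain.

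The endpoint in section 8.1.1 is density change at 3 and 6 months. An exit density taken at some other time enters the ITT analysis without being assigned to either time point. Table 1 in section 5.6 (oral tamoxifen, n=32) shows a mean change of -1.8 points at 3 months, -2.3 at 6 and -3.0 at 9, the last after treatment had stopped. If topical endoxifen behaves similarly, an early exit value tends to understate the scheduled one.

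At stake is the primary objective itself, an effect size for planning the next trial, and the go/no-go criterion mt-mc > 0%.

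**Working it through.** **The texts side by side**

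| Question | 9.1.2 | 9.1.3 | 10.6 | 10.7.11 |
|---|---|---|---|---|
| Woman uses too little product | not addressed | stays in, half effect | may be withdrawn, no re-entry | labelled not compliant |
| Woman stops the product | encouraged to stay, exit mammogram | not addressed separately | exit mammogram requested within 2 weeks | interruption over 14 days is discontinuation of treatment |
| Time point of the exit density | not stated | not modelled | not stated | not addressed |

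If section 10.6 were applied to every poor complier, up to 0.25 × 60 = 15 active-arm women would be withdrawn in addition to about 0.10 × 60 = 6 dropouts. Tables 4 and 5 do not describe that trial.

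**Inputs for sizing**
- Reduction of 12% of baseline density, the best guess in 9.1.3; 10% and 14% as variants.
- Mean baseline density 25.5% (9.1.3, time point 1, before the 240 lowest-density women were removed).
- Compliance split 65/25/10 (9.1.3), with dropouts counted as no reduction.
- SE of mt-mc: 1.55 points. This is an assumption, because the protocol gives none. It is checked against Table 4 next.

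**Reproducing the plan's figure.** Expected mt-mc = reduction × 25.5 × (0.65 + 0.25 × 0.5), and the false-negative probability at > 0 is Φ(−mean/1.55).

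| Reduction | Mean mt-mc | False negative | Table 4 |
|---|---|---|---|
| 10% | 0.10 × 25.5 × 0.775 = 1.98 | 10.1% | 10% |
| 12% | 0.12 × 25.5 × 0.775 = 2.37 | 6.3% | 7% |
| 14% | 0.14 × 25.5 × 0.775 = 2.77 | 3.7% | 3% |

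The adopted row is reproduced within 1 percentage point.

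**Withdrawing all poor compliers, 12% reduction**
- At month 3 with the value frozen. Table 1 gives 1.8/2.3 = 0.78 of the 6-month change by then. Mean = 0.12 × 25.5 × (0.65 + 0.25 × 0.5 × 0.78) = 2.29, which is 3.5% lower. False negative Φ(−2.29/1.55) = 7.0%.
- Retaining a quarter of the effect: 0.12 × 25.5 × (0.65 + 0.0625) = 2.18, which is 8% lower. False negative 8.0%.
- Contributing nothing: 0.12 × 25.5 × 0.65 = 1.99, which is 16% lower. False negative 10.0%.

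**Cross-check by simulation.** This used 20,000 trials per scenario, a gamma baseline density truncated above 2%, and dropout proportional to response. The SE was 1.43, taken from the first column of Table 5 read as the 0% null (its printed headings repeat those of Table 4).
- As planned: 9.3% / 5.8% / 3.3% false negatives at 10/12/14%, within 2 points of Table 4. Mean mt-mc at 12% is 2.19.
- Poor compliers withdrawn, exit mammogram capturing half of their reduction: mean 1.98 and false negatives 7.7% at 12%.
- Capturing none of it: mean 1.80 and false negatives 9.8% at 12%.

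Both routes give a small to moderate loss.

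**The case against.** Several stronger readings are tempting, and the documents do not support them.

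- *The exit mammogram contradicts the ITT plan.* It does not. Section 9.1.2 prescribes it and uses it. Nor does 9.1.2 promise 3- and 6-month mammograms after stopping; women are encouraged to remain, no more. The conflict is between withdrawing a woman and encouraging her to stay.
- *The exit value replaces both scheduled outcomes.* No text assigns it to a visit. Sachets are counted at the month 3 and month 6 visits, when mammograms are also due. Non-compliance found by counting at month 3 puts only the 6-month value at risk; at month 6 nothing is lost. Earlier withdrawal would have to come mainly from the month 1 questionnaire or direct contact.
- *The effect size is biased by 16%.* That needs all 25% poor compliers withdrawn and contributing nothing. Section 10.6 sets no threshold, the 80% and 14-day rules do not trigger study withdrawal, and section 10.5.8 has staff contact women to ensure compliance.
- *Withdrawals for non-compliance will differ by arm.* Section 6.3.2 excepts skin problems from the lack of dose dependency. That rests on six women per active dose with no severe skin problems, and withdrawal for side effects has its own criterion. This is possible but not shown.

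It is also fair to say that the trial is an unpowered pilot with a per-protocol analysis planned.

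All of this limits the size of the effect. It does not resolve the conflict between the sections or give the exit mammogram a time point.

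**Conclusion.** The point holds as a conflict in the text and a gap in the endpoint definition. Stopping the product is not separated from leaving the study. Non-compliance, undefined, can end scheduled follow-up without re-entry, and an off-schedule density can enter the 3- or 6-month ITT comparison. A woman withdrawn at or after month 3 loses only her 6-month value.

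The consequence at a 12% reduction is illustrative: a loss in mt-mc of about 3.5% to 16%, with false negatives of about 7% to 10% against about 6%. Both ends assume that every poor complier is withdrawn. The lower end also assumes the oral-tamoxifen time course, and section 5.6 itself notes that topical uptake could be slower. If fewer are withdrawn, the effect is smaller. No bias is demonstrated, but the wording should be corrected because the effect size is what this pilot is meant to deliver.

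**What to change.** Reconcile sections 9.1.2, 10.6, 10.7.11 and Appendix A:

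1. State that non-compliance, or stopping the product, does not by itself end outcome follow-up. The criteria for stopping treatment remain with the sponsor and investigator.
2. Ask every randomised woman who has not withdrawn consent to attend the scheduled 3- and 6-month mammograms, and use those in the ITT analysis.
3. Take an exit mammogram only when a scheduled one is declined, and analyse it labelled with its actual time since baseline.
4. Give Appendix A separate entries for women off treatment but in follow-up and for women withdrawn from the study.

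The cost is protocol wording, a little more follow-up effort, and at most one extra low-dose mammogram for a woman who stops early (two scheduled examinations instead of one exit examination). Section 6.4 limits images to reduce radiation, so that extra examination should be acknowledged there.

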10.7 Treatments

[figure not shown]
10.7.1 Identity of Investigational Medicinal Product (IMP)

The IMP, Topical endoxifen and its matching placebo, are formulated from widely used for both cosmetics and pharmaceutical topical constituents: Transcutol™ (2-(2-Ethoxyethoxy)ethanol); isopropanol, CrodamolTM GTCC (a fully saturated emollient triester) and mineral oil. The active IMP also contains endoxifen, the strength of which is based on Z-endoxifen content.

The formulated product is dispensed into single-dose (a dose defined as one administration per breast) and use "sachets". Each sachet is pliable and consists of laminated plastic and aluminum film. This configuration has been used for other topical pharmaceutical dosage units. Each sachet is fully sealed, labelled and sufficiently filled to deliver no less than 1.0 mL. Each sachet has a "nozzle" to facilitate the delivery of the product directly to the skin. It can be described as similar to a ketchup or mayonnaise packet for individual use at a restaurant (please also see more detailed description in the Investigator Brochure).

All investigational product (endoxifen and matching placebo) are manufactured according to Good Manufacturing Practice (GMP).

10.7.2 Flow of IMP from manufacturing to Investigators site

10.7.3 Packaging and labelling of IMP

The packaged Active Pharmaceutical Ingredient (API) is tested and released for shipment to PharmaProPackaging (PPP), Melbourne AUS, for drug product manufacture. Upon receipt by PPP, the identity of the API is confirmed, and used to manufacture the IMP, both the active and the placebo, and packaged into individual sachets according to GMPs. Each IMP is labelled with:

Each sachet (primary package) is labelled with:

- Atossa Genetics, USA
- 1 mL: 10 mg endoxifen or 5 mg endoxifen or placebo
- Topical, 1 sachet/breast /day
- Study: ATOS-010

- Rand.id: KCxxxx-x
- Batch Nr: xxx/xxx

Labelling is performed throughout the manufacturing process to limit the potential for mix-ups, in accordance with Good Manufacturing Practices (GMP).

Secondary packaging is labelled with same information as above with the additional information:

- Only for Clinical trial use
- Contains 184 sachets 1ml/sachet
- Storage instructions
- Sponsor: Atossa Genetics Inc. (contact information)
- Contact information Principal Investigator
- Expiry date: mm/yyyy

Size of labels and precise Swedish wording is to be found in Enclosure Labels in application to MPA.

10.7.4 Storage of IMP

When released the IMP will be stored at Apoteket Kliniska prövningar, Karolinska Sjukhuset, Solna.

They will store the IMP in the containers in which they are received from the Sponsor's supplier at room temperature. Extreme temperatures (hot, cold) should be avoided and the drug kept away from children.

10.7.5 Doses and treatment regimens

Participants will be randomized into one of three groups:

- Topical endoxifen, total 20 mg/day (10 mg/breast/day)
- Topical endoxifen, total 10 mg/day (5 mg/breast/day)
- Placebo 0 mg

Each participant will apply the contents of two sachets to each breast (one sachet/breast) each day for 6 months.

10.7.6 Investigational Medicinal Product accountability

The IMP will be dispensed to the study participant at baseline. A sufficient amount will be provided for at least 3 months. The number of sachets given out will be recorded in both CRF and in the Product Accountability log in the Study file. Participants are requested to bring back the empty sachets at the planned visits by 3 and 6 months or, by discontinuation, at time of exit examination. Any unused sachets will be saved for drug accountability and sent for destruction or to the manufacturer for analyses if directed by the sponsor.

10.7.7 Method of assigning participants to treatment groups

- A sequential list of participant identifiers (Rand.id) will be generated by the Investigator, and provided to the sponsor.
- Renaclinical LTD London will populate the sequential list of Rand.id and link dose of IMP (0 mg, 5 mg/sachet or 10 mg/sachet) to Rand.id in a randomized manner. A Randomization list is subsequently created.
- Renaclinical will provide the Randomization list directly to the pharmacy (Apoteket AB, Sjukhusapoteket Linköping) in a secured fashion, to be opened in case of a safety emergency.

- Renaclinical will also provide the Randomization list directly to PPP for blinded labelling and packaging.
- The IMP will be imported and received by Renaclinical. Once released by the QP, it will be sent to Apoteket Kliniska prövningar, Solna.
- IMP will be delivered to study site (Karma Study Centre) already randomized, packed and marked in a sequential order. The IMP will be provided to each participant in numerical order.
- The Investigator link the Rand.id to participant in the eCRF and Drug accountability log

Researchers do not have access to the Randomization list. In case of an emergency, the entire list will not be released, rather the treatment assigned for a specifically identified participant.

10.7.8 Blinding

The study is a double-blind, placebo controlled randomized study and neither the investigators, sponsor nor the participants will know who is on active treatment or placebo.

The randomization code (emergency envelope) is held by Apoteket AB, Sjukhusapoteket Linköping. The treatment code can only be broken if an investigator considers there is a valid medical or safety reason to break the blinding (see section 14.2 Emergency un-blinding, for further instructions). The Investigator must have a reason to break the blinding, for example when the studied drug is likely to have a significant effect on the clinical management of the study participant. When the code is broken for an individual participant, a notification must be made in the eCRF, and to the Principle Investigator and the Sponsor.

The study is also blinded for those responsible for mammographic density measurements.

10.7.9 Prior and concomitant therapy

All concomitant therapy must be recorded in the eCRF. No other drug under investigation may be used concomitantly with the study medication.

Although endoxifen is one of the first pass metabolites of tamoxifen, conditions that require medications metabolized by the P450 pathway should be carefully monitored during this study.

10.7.10 Prohibited medications

- Estrogen and progesterone based hormone replacement therapy (other than local), are not allowed during the study or used at study enrolment. Rationale for prohibition is potential interference with outcome measurements.
- Prescribed and regular use of anticoagulants (defined as substances included in group B01A in the ATC-system) are not allowed during the study or at time of study enrolment. Prescription of anticoagulants indicates that person is at risk of thrombosis. The literature and tamoxifen product information also describe concomitant use of tamoxifen and warfarin as a contraindication, since this combination may result in an increase in the anticoagulation and the risk of bleeding complications. Since the exact mechanism triggering this effect is not clear, the Sponsor declares the same precautions regarding endoxifen.
- Non-medical approved drugs against hot-flushes including phytoestrogen are not allowed during the study or used at study enrolment. Rationale for prohibition is potential interference with outcome measurements.

10.7.11 Treatment compliance

Compliance will be assessed throughout the study by: *i*) calculating the number of sachets remaining at the visits to the Karma Study Centre and comparing with the expected usage; and *ii*) by web-

questionnaires targeting adherence to therapy. The participant is defined as “compliant” if more than 80% of the sachets are used.

A maximum of 14 days of coherent treatment interruption is allowed. Longer time period than that must be seen as discontinuation of treatment.

11 ADVERSE EVENTS

11.1 Definitions

11.1.1 Adverse Event (AE)

Any untoward medical occurrence in a participant, who has received IMP, will be registered. The occurrence does not necessarily have to have a causal relationship with the IMP. An AE can therefore be any significant change, unfavourable and/or unintended sign (e.g., an abnormal laboratory finding), symptom, or disease temporally associated with the use of an IMP, whether or not considered related to the IMP.

11.1.2 Serious Adverse Event

An SAE is any untoward medical occurrence or event, at any dose, that:

- Results in death
- Is life threatening
- Requires hospitalization or prolongation of existing hospitalization
- Results in persistent or significant disability/incapacity

or

- Other important medical event (example of such events are convulsions that do not result in hospitalization)

Medical and scientific judgment should be exercised in deciding whether expedited reporting is appropriate in other situations, such as important medical events that may not be immediately life-threatening or result in death or hospitalization but may jeopardise the participant’s health or may require intervention to prevent one of the other outcomes listed in the definitions above. These AEs should also usually be considered as *serious*.

It is important to distinguish between serious and severe adverse events. Severity is a measure of intensity whereas seriousness is defined by the criteria in the previous sections. An adverse event of severe intensity need not necessarily be considered serious. For example, nausea, which persists for several hours, may be considered severe nausea but not a serious adverse event. On the other hand, a stroke resulting only in limited degree in disability may be considered a mild stroke but would be considered a serious adverse event.

11.1.3 Suspected Unexpected Serious Adverse Reaction (SUSAR)

A SUSAR is a suspected unexpected serious adverse reaction, potentially causally related to the investigational medicinal product, and will be reported to the appropriate IEC and Regulatory Authorities.

11.2 Registration and Assessment of AEs

Adverse Events will be collected through the web-based questionnaire each study participant must complete at a regular basis (month 1, 3 and 6) after study entry during the study period. Additionally, the participants are encouraged to report AEs anytime (24 hours/day and 7 days/week) to the Karma

Study Centre by contacting through phone, mail, visit or using the application Karmapp. All AEs, serious and non-serious, will be recorded in the eCRFs.

11.3 Eliciting and recording of AEs

Adverse Events will be collected through the web-based questionnaire each study participant must complete at a regular basis (month 1, 3 and 6) after study entry during the study period. Additionally, the participants are encouraged to report AEs anytime (24 hours/day and 7 days/week) to the Karma Study Centre by contacting through phone, mail, visit or using the application Karmapp. All AEs, serious and non-serious, will be recorded in the eCRFs.

